Diagnostic Stewardship for Ventilator Associated Pneumonia

Description of Outcomes and Statistical Analysis Plan

NCT05989269

August 11, 2023

Specific Aim 1: In a cluster-randomized crossover trial among 6 ICUs across 3 medical centers, evaluate the impact of a VAP diagnostic stewardship intervention on antibiotic use, VAP diagnoses, and adverse events.

Hypothesis: We expect a reduction in unnecessary antibiotics for VAP and in VAP clinical diagnoses in the intervention vs. control periods across all sites, without an increase in adverse events.

Primary Outcome: The primary efficacy outcome is reduction in proportion of unnecessary antibiotic therapy for presumed VAP in the intervention (modified reporting) period compared to control (standard reporting period), among patients not meeting clinical criteria for pneumonia and with growth of one or more organism(s) not considered normal upper respiratory flora.

Antibiotic action based on index culture result will be classified as follows:

- a) Not on empiric antibiotic(s), new antibiotic started based on index respiratory culture result, completed course for VAP
- b) Not on empiric antibiotic(s), no new antibiotics initiated based on culture result
- c) On empiric antibiotic(s), changed based on index respiratory culture, completed course for VAP
- d) On empiric antibiotic(s), continued without change following index respiratory culture, completed course for VAP
- e) On empiric antibiotic(s), antibiotics discontinued based on culture results
- f) On empiric antibiotics(s), but this therapy was not directed at the results of the index respiratory culture, and was not directed towards VAP

For patients where culturing was deemed inappropriate, antibiotic use in categories a, c, and d will together be considered “unnecessary antibiotic therapy for presumed VAP”

Note: Multiple respiratory cultures from the same patient may be eligible for intervention i.e., modified reporting during the intervention period. However, clinical outcomes linked to an “index respiratory culture” will be assessed using a single randomly selected respiratory culture from each included patient.

Secondary outcomes are as follows:

1. Antibiotic consumption outcomes: The following three outcomes will be measured to understand the impact on antibiotic use in ICU patients
 - a. Duration of antibiotic therapy: The duration of antibiotic therapy for possible or presumed VAP among patients who underwent intervention during the intervention period and among patients eligible for intervention in the control period will be compared. Duration of antibiotic therapy will be collected for all categories above (except b), and defined as uninterrupted days of therapy, irrespective of the number of different antibiotics, for the same episode of presumed VAP, assessed at discharge or day 28 whichever occurs first. For patients in category b, duration will be zero.
 - b. Antibiotic consumption during study intervention and control periods will be collected as antibiotic days of therapy (DOTs) as defined by CDC (Centers for Disease Control) NHSN as number of days that patients receive an antibiotic agent during a calendar day. The DOT for a given patient receiving multiple antibiotics on the same calendar day will

be the sum of the DOT for each antibiotic. This will be standardized to patient census of 1,000 patient days.

- i. Unit-level total antibiotic days of therapy (DOT) per 1,000 ICU patient-days: These data will be obtained from the hospital antimicrobial stewardship programs and will be compared in aggregate between the intervention and control periods for all study ICUs combined, and by hospital.
 - ii. Unit-level respiratory antibiotic DOT: This will be captured from the EMR by counting antibiotics that are ordered for “respiratory infection” indication starting at day 3 or later of ICU stay and expressed as days of therapy per 1,000 ICU patient-days. We will validate this outcome by chart review of a small sample of patients. These will be compared in aggregate between the intervention and control periods for all study ICUs combined, and by hospital.
2. Clinical diagnoses of VAP within 7 days after the index culture - measurement of this outcome will help understand how modification of reporting would influence the likelihood of a patient receiving a diagnosis of VAP. Because there are no consensus definitions for VAP, we will use the treating clinician’s documentation of pneumonia or VAP and treatment for those conditions to capture this outcome. The clinical diagnosis of VAP is an intermediate outcome that precedes the endpoint of antibiotic use. Clinical diagnoses of tracheobronchitis within 7 days after the index culture will also be recorded.
 - a. We will perform a sensitivity analysis of the impact on antibiotic use outcomes after excluding patients diagnosed with tracheobronchitis within 7 days of index culture. The hypothesis is that the intervention will have limited impact on those diagnosed and treated for ventilator-associated tracheobronchitis, and thus, we may see a larger difference between intervention and control when excluding patients with diagnoses of tracheobronchitisVentilator-free days: Ventilator-free days is defined as the number of calendar days within 28 days after the index respiratory culture on which the patient was not mechanically ventilated. Any patient dying within 28 days of the index respiratory culture collection will be assigned zero ventilator-free days. Ventilator-free days will be compared between the intervention and control periods for all study ICUs combined, and by hospital.
3. Rate of requests for complete reports in the intervention period – these data are applicable in the intervention period only. This will be a primarily descriptive analysis to help us understand if the intervention worked as intended i.e., how frequently did clinicians still want the full report with organism identification despite the nudge to consider asymptomatic colonization.
4. Adverse event outcomes: Death, bacteremia, and septic shock (from any cause) within 7 days of the index culture order will be recorded as potential significant adverse events from a delayed or missed true VAP diagnosis or delay in initiation of appropriate antimicrobial therapy, similar to methods described by Daley et al.¹ Incidence of these events will be compared between intervention and control periods individually for each event, and as a combined adverse event outcome. Two-person adjudication will be used to determine whether the above events were attributed to the intervention, during the intervention period.

Statistical methods for Aim 1:

Descriptive analyses using the Wilcoxon rank-sum test for continuous variables and the chi-square or Fisher’s exact tests for categorical variables will be used to compare patient-level data across each intervention arm. Analyses will be conducted on an intention-to-treat basis and will account for the cluster-randomized crossover design to ensure correct type I error rates and confidence intervals (CIs). A significance level of 0.05 will be used for all statistical comparisons.

Primary Outcome: The primary efficacy outcome is the reduction in proportion of unnecessary antibiotic therapy for presumed VAP in the intervention period i.e., modified reporting period compared to control period or standard reporting period, among patients not meeting criteria for culture order and with growth of one or more organism(s) not considered normal upper respiratory flora. Antibiotic therapy given for a culture that was collected in a patient not meeting algorithm criteria will be considered unnecessary (dichotomous outcome yes/no). For the primary outcome analysis (and all other patient-level analyses below), a patient will be included once in a given admission and the outcome will be assessed on the basis of a randomly selected qualifying respiratory culture during that admission (termed index respiratory culture). We will estimate the proportion of the primary outcome (i.e., unnecessary antibiotic therapy) in each intervention arm and will compare the two groups using risk difference from a generalized linear mixed model with an identity link function. The main analysis for the primary outcome will be intention-to-treat; a secondary per protocol (as treated) analysis will be done in which any cultures during the intervention period for which a modified report was requested but either the modification was not made, or the report was modified but the full report was released upon provider request or other reason, will not be included in the intervention group.

Power and Sample Size: For the population of ICU patients for which ordering of a respiratory culture has been determined inappropriate and there is growth of one or more organism(s) not considered normal upper respiratory flora, we test the effect of the diagnostic stewardship intervention on the proportion of antibiotic prescription in a two-period cluster-randomized cross-over design, where an ICU forms a cluster. The outcome follows a binary distribution with 50% probability to receive antibiotic prescription in the control group (pC). In a conservative estimate, we expect that the intervention reduces the probability by $\Delta = 0.15$ (= pC – pI) percentage points. Assuming the within-cluster within-period correlation is $\rho = 0.06$ and the within-cluster between-period correlation is about $\eta = 0.054$ ^{2,3} a total sample size of $N = 350$ in 6 ICUs across both periods is needed to detect an effect of $\Delta = 0.20$ with 85% power, using a generalized linear mixed model with random cluster, period, and cluster-period interaction effect. The computed total N is equivalent to a mean of about 5 patients per ICU per month, which is feasible in our experience. Given the uncertainty in predicting the actual number of patients that will be eligible to receive the intervention per ICU during the fixed 6-month period, we calculated the power for varying range of effect sizes and total N (Table).

Option	Power	Proportion control	Proportion intervention	N patients eligible for intervention per ICU per period*	Within-cluster within-period rho	Within-cluster between-period rho	Total N
1.	90%	50%	35%	30	0.06	0.054	619
2.	85%	50%	35%	30	0.06	0.054	547
3.	80%	50%	35%	30	0.06	0.054	493

4.	90%	50%	30%	30	0.06	0.054	390
5.	85%	50%	30%	30	0.06	0.054	350
6.	80%	50%	30%	30	0.06	0.054	322
7.	90%	50%	25%	30	0.06	0.054	285
8.	85%	50%	25%	30	0.06	0.054	261
9.	80%	50%	25%	30	0.06	0.054	243

Cluster- and participant-level covariates at baseline will be reported within each intervention arm. Adjusted analysis of the primary outcome will be performed as needed to control for differences in possible influential factors between intervention arms at baseline.

Statistical Methods for Secondary outcomes:

Generalized linear mixed models with a random cluster, period, and a cluster-period interaction modeling a negative binomial distribution will be used to compare the antibiotic duration count outcomes assessed at the participant-level (i.e., duration of therapy) between the intervention vs the control ICUs. The Wilcoxon rank-sum will be used to compare differences in antibiotic duration outcomes assessed at the ICU-level (total and respiratory antibiotic DOT) across intervention arm. Similar to the primary outcome model, generalized linear mixed model with random cluster, period, and cluster-period intervention effect will be used to compare other binomial participant-level outcomes (i.e., adverse events) across intervention arm. No adjustment for multiple comparisons will be made for secondary outcomes, therefore results should be considered exploratory.

Specific Aim 2: Evaluate overall impact of intervention including clinical and antibiotic outcomes using the "Desirability of Outcome Ranking (DOOR)/ Response Adjusted for Duration of Antibiotic Risk (RADAR)" methodology.

Aim 2a: Apply DOOR/RADAR methodology to measure outcomes of specific Aim 1

Hypothesis: We expect better overall patient outcomes (better DOOR ranking, accounting for duration of antibiotic use) in the intervention vs. control period.

Strategy: We will determine the probability that a patient who received the intervention has a better outcome than a participant who received the standard treatment. The clinical outcome of a participant will be ranked according to the table, from most (lower rank) to least (higher rank) desirable outcome, to obtain a 5-level ordinal outcome. We will conduct pairwise comparisons of each intervention patient to each control patient using two rules: When comparing patients with different overall clinical outcomes, the patient with a better overall clinical outcome based on the ranks in the below Table (Table 2) is determined to have the better outcome. When comparing two patients who have the same rank based on overall clinical outcome, the patient with a shorter course of antibiotics has the better outcome. Therefore, clinical outcome outranks the duration of antibiotic use i.e., a patient with a worse clinical outcome cannot have a better rank than a patient with a better clinical outcome, regardless of the duration of antibiotics.⁴ The duration of antibiotic therapy for possible or presumed VAP in relationship to the index respiratory culture (see above) will be used as the antibiotic duration measure for this analysis. Note that some patients will be on antibiotic therapy for reasons other than VAP - category f above. Thus, our antibiotic use duration may be more conservative for RADAR than studies that only look at antibiotics for the specific clinical entity, but this strategy helps to avoid overestimating

the impact on ICU antibiotic use in general. We will plan to conduct a sensitivity analysis with duration of antibiotic use defined with and without category f.

Table 2. Proposed DOOR criteria rank ordered by desirability of outcome

Rank	Objective clinical outcome (must meet each criterion listed for rank)
1	Discharged home by day 14, and not readmitted between days 15-28
2	Discharged home by day 14 but readmitted between days 15-28 Discharged to facility without ventilator by day 14, and not readmitted between days 15- 28 Off ventilator by day 14 and discharged home between days 15-28
3	Discharged to facility on ventilator by day 14 and not readmitted between days 15-28 Discharged to facility without ventilator by day 14 but readmitted between days 15-28 Off ventilator by day 14 and still in hospital between days 15- 28 Off ventilator by day 14 and discharged to facility between days 15-28 On ventilator > day 14 and discharged home between days 15-28
4	Discharged to facility on ventilator by day 14 and readmitted between days 15-28 On ventilator > day 14 and discharged to facility between days 15-28 On ventilator > day 14 and still in hospital between days 15- 28
5	Died in-hospital or designated for hospice care by day 28

Statistical methods for Aim 2a: The DOOR/RADAR probability represents the probability that a randomly selected patient who received the intervention has a better outcome than a randomly selected participant who received the standard reporting (control) accounting for antibiotic length of therapy. For each participant in an intervention cluster (ICU), the number of participants with a less desirable DOOR rank than that participant from the same ICU but during the control period will be determined. Results are then summarized across all 6 ICUs and the DOOR probability will be computed. Inverse probability weighting methodology using patient clinical characteristics may be applied to account for potential confounding.

In addition to the DOOR analyses just described, a two-dimensional analysis of the DOOR probability and difference in the mean duration of antibiotic use in the intervention and control groups will also be performed. Only subjects with non-missing DOOR and number of days on antibiotics will be included in these analyses. The horizontal axis will be the DOOR probability (probability of a more desirable outcome when assigned to intervention vs control) based on the 5-level ordinal DOOR outcome ignoring the duration of antibiotic use. The vertical axis is the difference in the means of the observed duration of antibiotic use (intervention minus control). A result in the lower right quadrant represents more desirable results for standard reporting (control), while a result in the upper left represents more

desirable for modified reporting (intervention). The other two quadrants represent tradeoffs for clinical outcomes and antibiotic use.

Aim 2b: Compare results of standard outcome analysis to those of DOOR analysis.

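### In patients not on empiric antibiotics, a completed VAP course counts as a primary event only if attributed to the index culture report, and that report differs between arms

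*SAP*

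**What the plan says.** The Primary Outcome text under Specific Aim 1 sorts antibiotic action after the index culture into six categories, a to f. It then says that "antibiotic use in categories a, c, and d will together be considered" unnecessary therapy for presumed VAP, so b, e and f are non-events.

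Two categories cover patients not on empiric therapy:

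- a, an event: "Not on empiric antibiotic(s), new antibiotic started based on index respiratory culture result, completed course for VAP"
- b, a non-event: "Not on empiric antibiotic(s), no new antibiotics initiated based on culture result"

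Among patients already on empiric therapy, c is a completed VAP course after a culture-based change, and d is "On empiric antibiotic(s), continued without change following index respiratory culture, completed course for VAP". Both are events. Category e (stopped because of the culture) and category f (not aimed at VAP) are non-events.

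Four other places bear on the point:

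- Secondary outcome 1a (duration of therapy): "For patients in category b, duration will be zero". Aim 2a uses this duration for the RADAR tie-break and for the vertical axis of the two-dimensional analysis.
- Secondary outcome 2 (clinical diagnoses of VAP within 7 days): "we will use the treating clinician’s documentation of pneumonia or VAP and treatment for those conditions to capture this outcome".
- Secondary outcome 3 shows what the modified report leaves out unless it is asked for. It will describe "how frequently did clinicians still want the full report with organism identification despite the nudge to consider asymptomatic colonization".
- Statistical methods for Aim 1, Primary Outcome, restates the event more loosely, as therapy given for a culture taken from a patient outside the algorithm criteria.

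**The concern.** The outcome is named for unnecessary therapy for presumed VAP, and everyone in the analysis population has already failed the criteria for culturing. Therapy is therefore equally unnecessary whatever prompted it. Yet in patients not on empiric therapy, a completed VAP course is an event only if someone judges that the culture result led to it. For patients on empiric therapy that judgement decides only between c and d, and both count.

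The judgement concerns a report that is itself the randomised exposure. Under standard reporting the organism is on the chart, and a later start is easily linked to it. Under modified reporting there is less to link it to. If starts are attributed to the report less often in the intervention period, some of the measured reduction would come from how courses are classified and not from fewer courses. The error would run in the direction of the trial's hypothesis. A treated patient placed in b would also contribute zero antibiotic days to the duration comparison and to DOOR/RADAR.

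**Working it through.** **Step 1. Classify one patient.** Take a patient not on empiric antibiotics who, after the report, starts and completes a course for VAP that is not attributed to the report.

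| Category | Does the patient fit? | Event? |
|---|---|---|
| a | No: the start was not based on the result | would be yes |
| b, as worded | Yes: nothing was started because of the result | no |
| b, if meant as no new VAP therapy | No: the patient was treated | – |
| c to f | No: these require empiric therapy | – |

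On either reading of b the course is not counted. On the literal reading its duration is also set to zero. A patient on empiric therapy whose regimen the culture did not change, and who completes a VAP course, is counted under d.

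**Step 2. Reproduce the plan's sample size, for scale.** The point does not rest on this figure. Inputs from Power and Sample Size: 50% versus 30%, 85% power, m = 30 patients per ICU per period, within-period correlation 0.06, between-period correlation 0.054. Alpha is 0.05 and is taken as two-sided, since the SAP does not say.

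- Variance inflation = 1 + (m − 1)(0.06) − m(0.054) = 1 + 1.74 − 1.62 = 1.12
- N = 2 × (1.960 + 1.036)² × (0.25 + 0.21)/0.20² × 1.12 + 4 × 30 = 231.3 + 120 = 351.3

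The SAP states 350. The same formula gives all nine table rows to within 2 patients, and 84.8% power at N = 350.

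**Step 3. Size of the spurious difference.** The SAP gives neither rate needed, so both are assumptions. Let q be the share of patients not on empiric therapy. Let u be the proportion of those who complete a VAP course not attributed to the report, in the intervention (I) and control (C) periods.

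Spurious difference = q × (u_I − u_C)

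- u_I = u_C: 0
- q = 0.5, u_C = 0, u_I = 0.10: 0.5 × 0.10 = 5 points, and 5/20 = 25% of the target difference
- q = 0.5, u_C = 0, u_I = 0.20: 0.5 × 0.20 = 10 points, and 10/20 = 50% of the target difference

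**Step 4. What this could do to the test.** Suppose there is no true effect and 50% complete a VAP course in each period. Let s be the share of those courses begun in patients not on empiric therapy, and f the share of those not attributed to the report. The spurious difference is 0.5 × s × (f_I − f_C). The chance of a significant result favouring the intervention uses the Step 2 formula at N = 350, with (350 − 120)/2 = 115 per arm after the 4m term. Nominally it is 2.5%.

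| s | f_C | f_I | Spurious difference | Chance of a significant result |
|---|---|---|---|---|
| any | 0.1 | 0.1 | 0 | 2.5% |
| 0.2 | 0 | 0.25 | 2.5 points | 5.5% |
| 0.4 | 0.1 | 0.3 | 4 points | 8.3% |
| 0.4 | 0 | 0.5 | 10 points | 30% |

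For the 10-point row: SE = √((0.25 + 0.24) × 1.12/115) = 0.0691; 0.10/0.0691 − 1.960 = −0.512; the normal probability below that is 0.304.

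**The case against.** Five arguments have force.

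1. *Treatment begun without relying on a culture is what empiric usually means.* A course started after collection but before the report may be classed as empiric and counted under c or d. This stands, and it confines the gap mainly to courses begun after the report. It does not remove the gap, because the SAP does not say when empiric status is assessed.

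2. *The result is not simply withheld.* A reader might infer that the same treated patient is necessarily an event in control and a non-event in intervention. The SAP does not support that. A modified report is still issued, the full one can be released on request, and such patients stay in the intervention group under intention-to-treat. A start after either report could be judged to rest on the culture. Unequal attribution is therefore a risk, not a certainty.

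3. *Zero days for category b suggests that b was meant as no VAP therapy at all, and the Statistical methods wording is looser.* This is probably the intent. But the treated patient then fits no category and is still outside a, c and d. Therapy given for a culture remains tied to the culture and does not say where an unattributed course goes.

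4. *The size is not documented, and control-period starts can also go unattributed.* Both are correct. Only the difference between periods biases the result, and zero is a possible value.

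5. *Secondary outcome 2 differs by intent.* The SAP calls it an intermediate outcome, so disagreement with the primary is not in itself a defect. It and unit-level respiratory DOT could help to reveal misattribution, but neither corrects the primary result.

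**Conclusion.** The concern holds in this form. For patients not on empiric antibiotics, event status turns on attribution to a report that differs by arm, while c and d count completed VAP courses whether or not the culture changed the regimen. An unattributed course begun after the report is not counted on any reading of b. The rule can therefore produce a spurious reduction, and the zero duration can carry it into the duration and DOOR/RADAR results.

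The size cannot be taken from the SAP. It is zero with equal non-attribution. It is 0–10 percentage points, against the 20-point difference behind N = 350, if half the patients are not on empiric therapy and 0–20% of those in the intervention period, none in control, start an unattributed VAP course. A reader might infer that the whole 20 points could be an artefact. Under the null scenario that would need 80% of courses to begin in patients not on empiric therapy and half of those to go unattributed in the intervention period only (0.5 × 0.8 × 0.5 = 0.20). Nothing in the SAP supports such rates. The definition should be changed, but the document does not show that the trial's effect would be mostly misclassification.

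**What to change.** - State the time point at which a patient is classed as on or not on empiric antibiotics.
- Define a and b by the target of therapy, in the same words for both periods:
  - a: not on empiric antibiotics at that time point; new antibiotic started for clinician-documented pneumonia or VAP within 7 days after the index culture (the window and documentation rule of secondary outcome 2) and completed as a VAP course, whether or not the result prompted it.
  - b: no such completed course. Set duration to zero only when no antibiotic for presumed VAP was given; otherwise record the actual days.
- Keep the completed-course condition in a. Without it, a course started and soon stopped would be an event in a, while its counterpart among empirically treated patients, category e, is a non-event.
- Align the restatement under Statistical methods for Aim 1 with this definition.
- Report culture-triggered starts as a descriptive subset.

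The cost is wording in the SAP and the case report form. Documentation and treatment data are already collected for secondary outcome 2, and course completion is already needed for a, c and d. The downside is that some starts unrelated to the culture will count in both arms, which may make the effect slightly smaller.

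### Antibiotic duration is compared between patients who received the intervention and controls who were only eligible for it, against the plan's intention-to-treat rule

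*SAP*

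**What the plan says.** The description of the duration outcome (SAP, Secondary outcomes, 1a) states that duration "among patients who underwent intervention during the intervention period and among patients eligible for intervention in the control period will be compared". On how days are counted, it adds: "For patients in category b, duration will be zero". For the other categories the days are collected.

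Four other places bear on who is analysed:

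- **Statistical methods for Aim 1, opening paragraph:** "Analyses will be conducted on an intention-to-treat basis and will account for the cluster-randomized crossover design". No outcome is exempted.
- **Statistical methods for Aim 1, Primary Outcome:** "For the primary outcome analysis (and all other patient-level analyses below), a patient will be included once in a given admission". As to which culture counts, this paragraph specifies that "the outcome will be assessed on the basis of a randomly selected qualifying respiratory culture during that admission". Neither clause requires that the report was modified. The same paragraph describes a secondary as-treated analysis, for the primary outcome, that removes intervention-period cultures where "a modified report was requested but either the modification was not made" or where "the report was modified but the full report was released upon provider request".
- **Statistical Methods for Secondary outcomes:** duration is modelled at participant level and compared between intervention and control ICUs, with no restriction to patients whose report was modified.
- **Interim analyses:** the monthly review counts eligible cultures and cultures intervened upon as separate quantities.

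The note under the primary outcome also says: "Multiple respiratory cultures from the same patient may be eligible for intervention i.e., modified reporting during the intervention period".

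**The concern.** The rule in 1a conditions one arm on something that happens after the ICU-period has been assigned, namely whether the report was in fact modified. The control arm has no matching condition. Patients who were eligible but whose report went out unmodified are lost from the intervention period, while their counterparts in the control period stay in.

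An analyst could therefore build either of two datasets and cite the SAP for each: all eligible index cultures in both periods, or modified cultures against eligible cultures. Only the first is the randomised comparison.

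The literal reading also leaves two questions open. Does a report that was modified and then released in full count as having undergone the intervention? An ordinary reading says yes. And when a patient has several eligible cultures, must the randomly chosen index culture itself have been modified?

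The same duration measure is reused for DOOR/RADAR in Aim 2a. If it takes its population along, the problem follows it there.

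**Working it through.** **Step 1. Are the two terms synonyms in this plan?**

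| Place in the SAP | Intervention-period group | Control-period group |
|---|---|---|
| Secondary outcomes, 1a | received the intervention | eligible |
| Statistical methods for Aim 1 | as assigned | as assigned |
| Primary Outcome (methods), rule for all patient-level analyses | one random qualifying culture | one random qualifying culture |
| Primary Outcome (methods), as-treated analysis | selected by what was done | no matching selection |
| Statistical Methods for Secondary outcomes | intervention ICUs | control ICUs |
| Interim analyses | eligible and intervened-upon counted apart | – |

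They are not. The plan foresees modifications that were requested but not made, and it tallies the two counts separately. Item 1a stands alone in making selection by receipt the stated population for an outcome.

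**Step 2. The plan's own figure.** The concern disputes no stated number; N = 350 is used only for scale. With two-sided alpha 0.05 (sidedness is not stated), 85% power, 50% against 30%, 30 patients per ICU-period, and correlations 0.06 and 0.054:

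- design effect = 1 + 29 × 0.06 − 30 × 0.054 = 1.12
- unadjusted total = 206.5, times 1.12 = 231.3
- adding 4 × 30 = 120 gives 351.3, against the stated 350. This small-cluster term is inferred from the table.

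The sample size describes one population, eligible in both periods. With equal periods that is 175 each. Omitting 10% of the intervention period removes 175 × 0.10 = 17.5, about 18 patients; omitting 20% removes 35.

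**Step 3. What could one-sided omission do?** Assume no true effect. Inputs:

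- p = 0.50, share treated (categories a, c, d) in both periods; this is the plan's control rate
- q = share of eligible intervention-period patients omitted (assumed)
- t = share treated among those omitted (assumed)
- h = mean days in categories b, e and f, divided by the mean treated course (assumed). Only category b is set to zero, so h = 0 is the extreme case.

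Retained treated share: r = (p − q·t) / (1 − q).
False ratio of mean durations, intervention to control: [r + (1 − r)·h] / [p + (1 − p)·h].

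Worked case, q = 0.20, t = 0.80: r = (0.50 − 0.16) / 0.80 = 0.425. At h = 0 the ratio is 0.425 / 0.50 = 0.85. At h = 0.25 it is (0.425 + 0.14375) / 0.625 = 0.91. At h = 0.5 it is (0.425 + 0.2875) / 0.75 = 0.95.

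| q | t | r | h = 0 | h = 0.25 | h = 0.5 |
|---|---|---|---|---|---|
| 20% | 80% | 0.425 | 0.85 | 0.91 | 0.95 |
| 20% | 30% | 0.550 | 1.10 | 1.06 | 1.03 |
| 10% | 80% | 0.467 | 0.93 | 0.96 | 0.98 |
| 10% | 30% | 0.522 | 1.04 | 1.03 | 1.01 |
| 5% | 80% | 0.484 | 0.97 | 0.98 | 0.99 |
| 5% | 30% | 0.511 | 1.02 | 1.01 | 1.01 |
| any | 50% | 0.500 | 1.00 | 1.00 | 1.00 |

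In days: if the omitted patients average g days more therapy than those retained, the false difference is −q·g. At q = 10% and g = 1 to 4 days (assumed) that is −0.1 to −0.4 days; a negative g reverses the sign.

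**The case against.** The best defence is that 1a is a loosely worded outcome description and that the methods text governs. The methods for secondary outcomes compare duration by ICU with no restriction, and the general rule is intention-to-treat. That does show which reading was probably meant. But the plan sets no order of precedence, 1a is the text specific to this outcome, and intention-to-treat is restated only for the main primary analysis. The defence confirms that 1a is out of line; it does not reconcile the passages.

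Three narrower points have force:

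- **Index-culture rule.** The conflict here is less sharp than the one with intention-to-treat, because the sentence does not define a qualifying culture and choosing one culture per patient is compatible with either population. The question about patients with several cultures arises only under the literal reading.
- **DOOR/RADAR.** Statistical methods for Aim 2a forms groups by ICU and period and also speaks of assignment. Reference in Aim 2a to patients who received the intervention may be ordinary arm language. Any effect there is conditional.
- **Size.** q, t and h are all assumed. A high t mainly fits reports released on request, yet on an ordinary reading those still count as having undergone the intervention and would not be omitted. For modifications simply not made, the plan gives no link to intent to treat, so t near 50%, and hence no bias, is plausible.

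That secondary results are exploratory lowers the stakes. The plan says so because it makes no multiplicity adjustment, which does not settle who is analysed.

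**Conclusion.** The concern holds. As written, 1a defines the arms asymmetrically and conflicts with the intention-to-treat rule for Aim 1. Followed literally, it drops patients from one arm on a post-assignment event.

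The asymmetry and the intention-to-treat conflict rest on the text alone. The consequence does not: neither the direction nor the size of a bias can be established from the plan. The calculated ratios, 0.85 to 1.10 at 20% omission and closer to 1 at smaller shares, show only that a spurious difference in either direction is possible. If the omitted patients resemble the rest, there is none.

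The primary intention-to-treat analysis and the sample size are not affected. This should be corrected before analysis, but it does not threaten the trial's main result.

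**What to change.** In Secondary outcomes, 1a, define the duration population identically in both periods: all patients with an eligible index culture, analysed by the assigned ICU-period whether or not the report was modified or later released in full. Use the same population, and wording based on assignment, in Aim 2a (Strategy and Statistical methods).

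If a comparison restricted to patients who received the intervention is wanted, label it a supportive as-treated analysis. State there how released reports are classed and whether the index culture itself must have been modified.

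The cost is SAP wording only, since the primary intention-to-treat analysis already needs all eligible patients in both periods. The trade-off is that non-adherence may dilute the estimated effect on duration.
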